1 INTRODUCTION

HUMIRA®(adalimumab), a recombinant, full-length immunoglobulin is the first member of a new class of tumour necrosis factor (TNF) antibody compounds, developed to contain exclusively human sequences with a very high affinity for human TNF.

To date, more than 3,000 patients with rheumatoid arthritis (RA) have been treated subcutaneously with HUMIRA®(adalimumab) in controlled trials and more than 6,000 in phase IIIb studies and patient named basis programs in Europe, North America and Australia. HUMIRA®(adalimumab) was administered alone or in combination with methotrexate (MTX) or other disease-modifying anti-rheumatic drugs (DMARDs) or DMARD combinations.

HUMIRA®(adalimumab) has generally been well tolerated and has demonstrated therapeutic efficacy in the treatment of RA compared to placebo treatment. HUMIRA®(adalimumab) has also shown sustained efficacy in open-label long-term studies, however the data related to patients treated for four and five years is still limited (1, 2).

RA clinical development is largely completed although a number of long-term extension studies and studies for additional indications, e.g. Juvenile Rheumatoid Arthritis and early RA are ongoing.

HUMIRA®(adalimumab) was first approved by the Food and Drug Administration (FDA) for the treatment of patients with RA in the United States of America in December 2002, in Switzerland in April 2003, as well as in several Latin American countries. HUMIRA®(adalimumab) was approved in the European Union in September 2003. “HUMIRA®(adalimumab) is indicated for the treatment of moderate to severe, active rheumatoid arthritis in adult patients when the response to disease-modifying anti-rheumatic drugs including methotrexate has been inadequate. To ensure maximum efficacy, HUMIRA®(adalimumab) is given in combination with methotrexate. HUMIRA®(adalimumab) can be given as monotherapy in case of intolerance to methotrexate or when continued treatment with methotrexate is inappropriate”.

The data from the Psoriasis arthritis (PsA) controlled clinical trials support the conclusion that adalimumab has a favorable benefit/risk ratio in the treatment of subjects with PsA.

As from August 2005 EMEA has granted the approval for the use of Humira® (adalimumab) for the treatment of active and progressive psoriatic arthritis in adults when the response to previous disease-modifying anti-rheumatic drug therapy has been inadequate.

It is expected that as from June 2006 the indications of HUMIRA®(adalimumab) will be extended with the treatment of adults with active ankylosing spondylitis who have had an inadequate response to conventional therapy. This amendment will be of application after the indication has been approved by EMEA.

For this PMOS, the follow-up observation period is planned for 5 years and is focussed on safety information as well as maintenance of efficacy parameters for HUMIRA®(adalimumab) during normal clinical practice.

2 STUDY OBJECTIVES

The objectives of this post-marketing observational study are to:

Observe and assess the long-term use, safety and efficacy of HUMIRA®(adalimumab), as prescribed by the rheumatologist in a normal clinical setting and in accordance with the terms of the European marketing authorization.

Observational statistics will be made on:

- Eventual taper-off of concomitant medication (Corticosteroids and NSAIDs) when being treated with HUMIRA®(adalimumab).
- Evaluations on patient's non-medical complications (number of non-working days, number of days of hospitalization, ...)

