3 INVESTIGATIONAL PLAN

This is a multi-center, uncontrolled observational study of patients who at the time of entry were prescribed with HUMIRA®(adalimumab) following normal clinical practice, with or without other anti-rheumatic treatments, prior to enrollment in this study.

Patients will be followed for 5 years within the post-marketing observational study.

Physicians will be provided with a study kit that includes a protocol, patient informed consent forms, adverse event report forms, and Data Report Forms (DRFs), for each patient to be enrolled. The participating physician will already have provided a prescription to the patient for HUMIRA®(adalimumab), along with instructions for appropriate use according to the European Union (EU) Summary of Product Characteristics (SPC).

Once the physician has determined that the patient meets the inclusion criteria, and the patient has agreed to be included in the observational study, the patient's baseline demographic data, and disease status will be reported in the Baseline DRF. The physician will then follow-up the patient via regular office visits at intervals as determined by routine clinical practice or as recommended by national guidelines.

Patient's safety and efficacy data if they are part of clinical routine will be recorded in the DRFs at Baseline, and regular visits which are closest to Month 3, Month 6, Month 9, Month 12, Month 18, Month 24, Month 30, Month 36, Month 42, Month 48, Month 54, and Month 60. While the physician will likely deem it appropriate and necessary to have the patient return for intermediate visits during the study period, data will be collected via DRFs only at the intervals which correspond closely to those described above. Physicians are encouraged to treat their patients as they would in their routine clinical practice. If treatment with HUMIRA®(adalimumab) is permanently discontinued for any reason, patients will be discontinued from the study and the reason should be recorded. Physicians will be asked to record adverse events up to 3 months after last administration of HUMIRA®(adalimumab) on the DRF of the next scheduled data collection time.

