3.2.2 Efficacy Variables

Data on the following individual parameters will be collected if assessed as part of clinical practice at each site:

- 28 joint assessment

- physical function (HAQ)
- inflammatory parameter (ESR, CRP)
- concomitant medication
- change in concomitant steroids, NSAIDs
- assessment of non-medical complications (number of non-working days, number of days of hospitalization, ...)
 - for patients with polyarticular or oligoarticular erosive psoriatic arthritis:
 - % of the Body Surface Area (BSA) with psoriatic skin lesions
 - for patients with oligoarticular erosive psoriatic arthritis:
 - Numerical Rating Scale (score of 0 to 10) for the disease activity in the most important joint by the patient (0 = no disease activity during the previous days, 10 = maximal activity during the previous days)
 - Numerical Rating Scale (score of 0 to 10) for the disease activity in the most important joint by the physician (0 = no disease activity during the previous days, 10 = maximal activity during the previous days)
 - For patients with Ankylosing spondylitis the BASDAI will be measured

Table 1: Schedule of Study Assessments

Procedure	Day 1	Month* 3, 6, 9, 12, 18, 24, 30, 36, 42, 48, 54, 60
Informed Consent	✓	
Demographics	✓	
Safety Data Collection	✓	✓
Efficacy Data Collection	✓	✓
Concomitant DMARDs, steroids, NSAIDs	✓	
Changes in concomitant DMARDs, steroids, NSAIDs		✓
Data Report Form Completion	✓	✓

* Data collection at regular visits which are closest to time points described

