3.3.6 Primary Data Collection

The following safety information will be collected: adverse events and serious adverse events. The description of event, start and end date, severity, outcome, causal relationship, and action taken will be recorded.

Data to allow determination of patient's disease activity will be collected. These are 28 joint count of swelling and tenderness (SJC, TJC), physician's global assessment of disease activity, HAQ, ESR and CRP. These data, if available as a result of usual medical practice, will be collected via the DRFs.

Other Data

Changes in concomitant DMARDs, steroids, and NSAIDs as well as the administration schedule of HUMIRA® (adalimumab) should be documented in the DRFs.

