1. METHODOLOGY

The purpose of this statistical analysis plan is to provide detailed information on the statistical analysis of the data of the ProAct study. The plan is based on the quotation dated 18 October 2017 and the mail dated 4 April 2017.

1.1 *Study Objective*

To evaluate the effectiveness and safety of adalimumab for the treatment of rheumatoid arthritis (RA), psoriatic arthritis (PsA) and ankylosing spondylitis (AS) in real life clinical practice.

1.2 *Available data*

The questionnaires table, as received on 5 February 2018, contained 47378 records, of which 5947 baseline visits. This database has been adapted by hardcoding in the programmation in order to resolve inconsistencies, double patients, misclassification of visits, add additional visit CRF pages, add additional AE pages. A total of 5920 patients of which 2836 rheumatoid arthritis patients, 1127 psoriatic arthritis patients (of which 197 Oligoarticular PsA) and 1957 ankylosing spondylitis patients were included in the analysis.

The parameter DAS28 was entered in the database from the moment the new Belgium reimbursement criteria for Humira were in place (2010).

Visits were scheduled at baseline, months 3, 6, 9 and 12, then every 6 months till 5 years.

1.3 *Patient Population*

All patients are to be considered in the analysis.

1.4 *Data Handling*

All data handling rules used during the analysis will be described in the section Methodology of the Statistical Report.

‘LT’ visits are visits added in the database for patients who were lost to follow-up in order to close the patient in the database. These visits will not be taken into account for any analysis.

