1.5 Derived Data

- Study duration (year) = (visit date of last visit – visit date of baseline visit)/365.25

- Completed patients: patients with ≥ 1734 days study duration

- Treatment duration (year):

For completed patients:

(Date of last visit – Date of baseline visit)/365.25

For not completed patients:

Sum of number of weeks/52, months/12 and years patient has been on drug documented on the last visit

If missing: (Date of last visit – Date of baseline visit)/365.25

Note: Some patients stopped Humira temporally. The periods of not taken Humira are not taken into account for the analysis. These patients will be considered as having taken Humira during the complete study.

- Treatment duration category:

0 to 3 months

> 3 to 6 months

> 6 to 9 months

> 9 to 12 months

> 12 to 18 months

> 18 to 24 months

> 24 to 30 months

> 30 to 36 months

> 36 to 42 months

> 42 to 48 months

> 48 to 54 months

> 54 to 60 months

> 60 months

- For the purpose of the analysis of the evolution of parameters over time, follow-up visits will be classified into time windows, defined upon the number of days between Visit 1 and the date of each subsequent visit (PERIOD = Date of follow-up visit - Date of Visit 1)

- Period = Date of visit – Date of baseline visit

- Month 3 window: $1 \leq \text{period} \leq 137$ days

- Month 6 window: $138 \leq \text{period} \leq 228$ days

- Month 9 window: $229 \leq \text{period} \leq 319$ days

- Month 12 window: $320 \leq \text{period} \leq 456$ days

- Month 18 window: $457 \leq \text{period} \leq 639$ days

- Month 24 window: $640 \leq \text{period} \leq 821$ days

- Month 30 window: $822 \leq \text{period} \leq 1004$ days

- Month 36 window: 1005 <= period <= 1186 days
- Month 42 window: 1187 <= period <= 1368 days
- Month 48 window: 1369 <= period <= 1551 days
- Month 54 window: 1552 <= period <= 1733 days
- Month 60 window: 1734 <= period <= 1916 days

Each visit will be classified in a time window. If the date of the visit is completely missing, it will be assumed that the visit took place on the target day of the window as indicated on top of the follow-up page. If more than one follow-up visit is classified into the same time window, the visit closest to the target day is retained. If within a time window there are two visits at the same distance from the target day, the visit which comes first (e.g. before the target date) is retained. If there are two visits on the same date, the first record is retained.

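### The SAP has no follow-up table for two items on which the protocol promises statistics: steroid and NSAID taper-off, and non-working and hospitalization days

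*Protocol*

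**What the plan says.** Protocol section 2 follows its general objective with a commitment to observational statistics on two named items. The first is "Eventual taper-off of concomitant medication (Corticosteroids and NSAIDs) when being treated with HUMIRA®(adalimumab"). The second is non-medical complications, with the examples "number of non-working days, number of days of hospitalization".

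Both return as variables in Protocol 3.2.2, to be collected where they are part of a site's clinical practice. The medication item appears there as "change in concomitant steroids, NSAIDs". Table 1 of the protocol gives medication changes their own row, ticked for the Month 3 to Month 60 column. Protocol 3.3.6 asks for "Changes in concomitant DMARDs, steroids, and NSAIDs as well as the administration schedule" of adalimumab to be entered on the data report forms.

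SAP 1.1 states the objective as "To evaluate the effectiveness and safety of adalimumab for the treatment of rheumatoid arthritis (RA") and the other two indications, in real-life practice. SAP section 2 has a general sentence on how parameters evolve over time, which names none of them, and then lists the tables to be produced. Steroids and NSAIDs are in that list only as 1.7.1 and 1.7.2, under baseline characteristics. Non-working days and hospitalization days are not in it.

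**The concern.** Taper-off means that use at a later time is lower than use at the start. A baseline table holds only the first half of that comparison. For the day counts there is not even a baseline table. An analyst who follows the SAP exactly therefore produces nothing on either item, and a later reader cannot tell whether the data were missing, were analysed elsewhere or were overlooked.

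A careless repair carries its own risk. If treatment with adalimumab "is permanently discontinued for any reason, patients will be discontinued from the study". A table giving only the percentage on steroids in each window would thus describe a shrinking and selected group. It could rise or fall with no patient changing medication.

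**Working it through.** The plan states no figure on this point to reproduce. The check is a count of tables, followed by three short calculations that give context or shape the fix.

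**1. Count of follow-up tables (SAP section 2, lists headed Follow-up Data)**

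| Indication | 2.1 | 2.2 | 2.3 | Total | On steroids or NSAIDs | On non-working or hospitalization days |
|---|---|---|---|---|---|---|
| RA | 4 | 2 | 10 | 16 | 0 | 0 |
| PsA | 4 | 2 | 16 | 22 | 0 | 0 |
| AS | 4 | 2 | 13 | 19 | 0 | 0 |
| All | 12 | 6 | 39 | 57 | 0 | 0 |

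The tables cover treatment duration, physician's assessment, joint counts, CRP and ESR, HAQ and DAS28, with skin area and rating scales added for PsA and BASDAI for AS. The part for all patients together holds adverse event tables only. SAP 1.5 derives no variable for either item. The nearest output is table 3.6, reasons for seriousness. It may count events that were serious because of hospitalization, but it does not give days in hospital and says nothing on work loss.

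**2. Volume of follow-up data (context only)**

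SAP 1.2 says the questionnaires table "contained 47378 records, of which 5947 baseline visits".

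- Follow-up records: 47,378 − 5,947 = 41,431.
- Per baseline record: 41,431 / 5,947 = 6.97.
- Against the 12 scheduled follow-up visits: 6.97 / 12 = 58%.

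This assumes one record per visit. It uses the table as received, before corrections, and may include the LT closing visits. Patients who stopped adalimumab were not meant to reach 12 visits. It shows that follow-up records exist, not that they hold these two items.

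**3. Why a bare percentage per window would mislead (all inputs assumed)**

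Let p be the proportion on steroids at baseline, r the proportion of users still in the study, and s the proportion of non-users still in the study. No patient changes use. The observed proportion is

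p·r / [p·r + (1 − p)·s].

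With p = 0.40 and s = 0.60, (1 − p)·s = 0.36.

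| r | p·r | Observed percentage on steroids |
|---|---|---|
| 0.70 | 0.28 | 0.28 / 0.64 = 43.8% |
| 0.60 | 0.24 | 0.24 / 0.60 = 40.0% |
| 0.50 | 0.20 | 0.20 / 0.56 = 35.7% |
| 0.40 | 0.16 | 0.16 / 0.52 = 30.8% |

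True taper-off is zero in every row.

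**4. Why raw day counts per form would mislead**

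Scheduled spacing goes from 3 to 6 months after Month 12. At a constant true rate, days per form change by 6 / 3 = 2.0 if the form asks for days since the previous form, and by 1.0 if the recall period is fixed. The documents do not give the recall period. In the first case the SAP 1.5 window rule also loses days: "If more than one follow-up visit is classified into the same time window, the visit closest to the target day is retained". Days on the forms not retained would be dropped.

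**The case against.** Nobody reading the table list can dispute the omission. The case on the other side is about weight and scope.

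- **The two items are not equally supported.** Medication change has its own Table 1 row and a form instruction; non-medical complications have neither. This is fair as to strength of evidence. But Protocol 3.2.2 lists non-medical complications as efficacy variables, so Table 1's row for efficacy data at follow-up covers them.
- **Collection was conditional on clinical practice, so data may be thin.** True. HAQ, joint counts, ESR and CRP carry the same condition and all receive follow-up tables. Sparse data could justify dropping an item if the SAP said so; it does not.
- **The SAP's objective does not exclude the items.** Fair: the protocol classes both as efficacy variables, so the word effectiveness could cover them. The gap lies in the table list, and the general sentence on evolution over time does not close it.
- **Scope may have been settled in the quotation and mail on which the SAP is based.** Possible, since neither can be seen. The point is therefore limited to what this SAP plans, and a pointer to another report would answer it.
- **The drop-out and days-per-form figures criticise tables that do not exist.** They do. They do not measure the omission; they explain how the missing tables should be built. The 58% likewise carries no weight in the conclusion.
- **The protocol promises only descriptive statistics on supplementary items.** Correct, and it limits the severity.

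**Conclusion.** The concern holds. Two items on which Protocol section 2 promises statistics have 0 of 57 follow-up tables in the SAP, and no reason is given. The conclusion rests on the documents' text alone and needs no assumption. Whether the database holds enough data on either item cannot be told from the documents, and that decides whether the remedy is tables or an explanation.

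This should be fixed, but it is not critical: no listed efficacy or safety result is affected. What is lost is the promised description of steroid and NSAID taper-off on adalimumab and of days lost to work and hospital.

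**What to change.** Add a follow-up section 2.4 for each indication, with the number of patients with data shown in every table.

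- **(a) Steroids and NSAIDs, per window.** Give the percentage on each. Among baseline users, give the percentage who stopped and who continued, and who reduced if dose was recorded. Among baseline non-users, give the percentage who started. Show patients who have left the study as a separate category, so that drop-out cannot pass for taper-off.
- **(b) Non-working and hospitalization days.** State the form's recall period. If it is the time since the previous form, report days per patient-year from all follow-up forms, and say that the one-visit-per-window rule in SAP 1.5 does not apply to this table. If the recall period is fixed, report days per recall period.
- **(c) If an item is too incomplete to analyse, or is reported elsewhere,** say so in the SAP with the reason.

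The cost is a SAP revision and descriptive tables for two drug classes and two day counts in three indications, from whatever the database already holds. Where (c) applies, the cost is one sentence. No protocol amendment is needed.

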3 INVESTIGATIONAL PLAN

This is a multi-center, uncontrolled observational study of patients who at the time of entry were prescribed with HUMIRA®(adalimumab) following normal clinical practice, with or without other anti-rheumatic treatments, prior to enrollment in this study.

Patients will be followed for 5 years within the post-marketing observational study.

Physicians will be provided with a study kit that includes a protocol, patient informed consent forms, adverse event report forms, and Data Report Forms (DRFs), for each patient to be enrolled. The participating physician will already have provided a prescription to the patient for HUMIRA®(adalimumab), along with instructions for appropriate use according to the European Union (EU) Summary of Product Characteristics (SPC).

Once the physician has determined that the patient meets the inclusion criteria, and the patient has agreed to be included in the observational study, the patient's baseline demographic data, and disease status will be reported in the Baseline DRF. The physician will then follow-up the patient via regular office visits at intervals as determined by routine clinical practice or as recommended by national guidelines.

Patient's safety and efficacy data if they are part of clinical routine will be recorded in the DRFs at Baseline, and regular visits which are closest to Month 3, Month 6, Month 9, Month 12, Month 18, Month 24, Month 30, Month 36, Month 42, Month 48, Month 54, and Month 60. While the physician will likely deem it appropriate and necessary to have the patient return for intermediate visits during the study period, data will be collected via DRFs only at the intervals which correspond closely to those described above. Physicians are encouraged to treat their patients as they would in their routine clinical practice. If treatment with HUMIRA®(adalimumab) is permanently discontinued for any reason, patients will be discontinued from the study and the reason should be recorded. Physicians will be asked to record adverse events up to 3 months after last administration of HUMIRA®(adalimumab) on the DRF of the next scheduled data collection time.

3.1 Study Population

Patients with rheumatoid arthritis, psoriatic arthritis or ankylosing spondylitis who have been prescribed HUMIRA® (adalimumab) within local reimbursement guidelines for anti-TNF α 's may be enrolled in the study.

HUMIRA® (adalimumab) is used in a normal clinical setting according to label.

3.1.1 Inclusion Criteria

- Patients with ongoing HUMIRA® (adalimumab) treatment who have been prescribed HUMIRA® (adalimumab) within local reimbursement guidelines.

- Patients must be willing to consent to data being collected and provided to Abbott Laboratories

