3.3.4 Patient History

The physician will determine the patient's current status at the Baseline visit and record it in the Baseline DRF. The patient's status will also note concomitant conditions and whether or not these conditions are currently treated. Changes in concomitant medications being taken to treat RA should also be recorded.

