- BASDAI responder: a relative improvement in BASDAI of $\geq 50\%$
- DAS28 category: <2.6 , ≥ 2.6 and ≤ 3.2 , >3.2
- Serious adverse event = event where at least one criteria of seriousness is present
- An adverse event is considered to start in a certain year if the difference between start date and date of baseline (=AEPER) is in the following windows:
 - Year 1: $0 \leq \text{AEPER} < 365.25$
 - Year 2: $365.25 \leq \text{AEPER} < 730.5$
 - Year 3 $730.5 \leq \text{AEPER} < 1095.75$
 - Year 4: $1095.75 \leq \text{AEPER} < 1461$
 - Year 5: $1461 \leq \text{AEPER} < 1826.25$

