 - 1.7.4 Number of DMARDs Used
 - 1.7.5 Frequency of Use of Each Type of DMARD
 - 1.7.6 Combination of Types of DMARD Used
 - 1.8 Study Duration
 - 1.9 Results of the Tests

- 2 Follow-up Data**
 - 2.1 Treatment Duration
 - 2.1.1 Treatment Duration
 - 2.1.2 Treatment Duration Category
 - 2.1.3 Treatment Duration Broken Down by Year of Start Treatment
 - 2.1.4 Treatment Duration Broken Down by DAS28 Category at Window 2 (Month 6)
 - 2.2 Physician's Assessment of Disease Activity
 - 2.2.1 Physician's Assessment of Disease Activity in Each Window
 - 2.2.2 Physician's Assessment of Disease Activity - Difference from Baseline
 - 2.3 Clinical Examination
 - 2.3.1 Joint Assessment (tender joints count, swollen joints count) in Each Window
 - 2.3.2 Joint Assessment (tender joints count, swollen joints count) – Difference from Baseline
 - 2.3.3 Inflammatory Parameters (CRP, ESR) in Each Window
 - 2.3.4 Inflammatory Parameters (CRP, ESR) – Difference from Baseline
 - 2.3.5 Physical Function (HAQ %) in Each Window
 - 2.3.6 Physical Function (HAQ %) – Difference from Baseline
 - 2.3.7 Physical Function (HAQ %) - Number of Patients with >7.33% Reduction from Baseline
 - 2.3.8 DAS28 in Each Window
 - 2.3.9 DAS28 – Difference From Baseline
 - 2.3.10 DAS28 Category in Each Window

3 Adverse Events

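### Change-from-baseline and responder tables mix pre-treatment and on-drug baselines in unknown proportion

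*Protocol*

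**What the plan says.** **Entry.** Protocol 3.1.1 includes "Patients with ongoing HUMIRA® (adalimumab) treatment" if the prescription met local reimbursement rules. Protocol 3 describes "patients who at the time of entry were prescribed with HUMIRA®(adalimumab) following normal clinical practice" and places that prescription before enrolment. It adds that "The participating physician will already have provided a prescription to the patient". None of these passages limits the time between first dose and enrolment.

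**Baseline.** Protocol 3.3.4 states: "The physician will determine the patient's current status at the Baseline visit and record it in the Baseline DRF". This is status at enrolment. The protocol asks for no pre-treatment value of any efficacy measure.

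**Analysis.** SAP 1.3 includes all patients, and SAP 1.5 counts every visit window in days from the baseline visit. The table lists in SAP 2 give differences from baseline for physician's assessment, joint counts, CRP and ESR, HAQ and DAS28 in each indication. BASDAI is added for AS, and skin area (as a shift) and the numerical rating scales for PsA. There are two responder-type tables. One counts patients whose HAQ % falls by more than 7.33%. The other uses SAP 1.5: "BASDAI responder: a relative improvement in BASDAI of" at least 50%. That definition names no reference value, but the enrolment visit is the only candidate in the plan.

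**Treatment start.** It appears in one type of table only, "2.1.3 Treatment Duration Broken Down by Year of Start Treatment". The SAP does not define it and does not use it to split any effectiveness table.

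**The concern.** SAP 1.1 sets out to evaluate effectiveness in real-life practice. A change from baseline, or a 50% improvement, reads naturally as response to starting adalimumab. That reading is sound only if the baseline value was taken before or at about the first dose.

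For a patient already on the drug and already improved, Visit 1 is in effect a follow-up value. The later difference shows whether the improvement was kept, and a further 50% fall in BASDAI is much harder to reach. Pooling both kinds of patient gives a mixture whose size depends on an unreported share. A small mean change could reflect weak response in new starters or good maintenance in patients already treated, and the planned tables cannot tell these apart.

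**Working it through.** **1. Plan's own count.** SAP 1.2 gives 2836 RA + 1127 PsA + 1957 AS = 5920, which matches its stated total. There is no power calculation to reproduce and no count of patients on drug at baseline. BASDAI is tabulated only for AS, 1957/5920 = 33% of patients.

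**2. Could patients have been treated for some time?** Protocol 1 gives EU approval as September 2003 for RA and August 2005 for PsA, and expects AS from June 2006. By June 2006 on-label treatment could have lasted up to 33 months in RA and 10 months in PsA, and essentially no time in AS. Later AS enrollees could have been on drug longer. This shows that prior treatment was possible, not how common it was.

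**3. Mean change.** Let D be the mean change from pre-treatment to a given window, f the share of patients on drug at baseline, and r the share of D already reached by then. D is assumed equal in both groups. New starters show D and already-treated patients show (1 − r)·D, so

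pooled change = (1 − f)·D + f·(1 − r)·D = (1 − f·r)·D.

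Neither f nor r is in the documents. Over an assumed range, 1 − f·r is:

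| f | r = 0.25 | r = 0.5 | r = 0.8 |
|---|---|---|---|
| 0.10 | 0.975 | 0.95 | 0.92 |
| 0.25 | 0.938 | 0.875 | 0.80 |
| 0.50 | 0.875 | 0.75 | 0.60 |
| 1.00 | 0.75 | 0.50 | 0.20 |

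**4. BASDAI response.** Let q be a patient's relative improvement from pre-treatment. Measured from an on-drug baseline, the improvement is q·(1 − r)/(1 − r·q). This reaches 0.5 only if q ≥ 0.5/(1 − 0.5·r). At r = 0.8 the bar is 0.5/0.6 = 0.83 instead of 0.50.

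Assume q is normal with mean 0.5 and SD 0.3. Then P(q ≥ 0.50) = 50.0%, and P(q ≥ 0.83) = P(Z ≥ 1.11) = 13.3%. The pooled rate is (1 − f)·50.0 + f·13.3. A simulation of 400,000 patients used the same q (limited to −0.3 to 0.95) and an assumed pre-treatment BASDAI of mean 6.5, SD 1.3, limited to 4–10. It agrees within 0.2 points:

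| f (r = 0.8) | Formula | Simulation |
|---|---|---|
| 0 | 50.0% | 50.1% |
| 0.10 | 46.3% | 46.5% |
| 0.25 | 40.8% | 40.9% |
| 0.50 | 31.7% | 31.7% |
| 1.00 | 13.3% | 13.3% |

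The starting 50% is built in by centring q on the threshold. Only the fall from it is informative.

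**5. Late windows.** Under Protocol 3, patients who permanently stop adalimumab leave the study, so late windows hold persisters. Assume a change of −3.5 in persisters and −1.0 in stoppers.

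- At 60% persistence the all-patient change is 0.6·(−3.5) + 0.4·(−1.0) = −2.50. The persister-only table overstates it unless f·r exceeds 1 − 2.50/3.50 = 0.286.
- At 80% persistence it is 0.8·(−3.5) + 0.2·(−1.0) = −3.00, and the break-even is 1 − 3.00/3.50 = 0.143.

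With f = 0.25 and r = 0.8, f·r = 0.20 and the table would show −3.5·0.80 = −2.80. That overstates the all-patient change in the first case and understates it in the second.

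**The case against.** **Prior treatment may be rare.** Protocol 3 fits enrolment at or just after prescription, Table 1 calls baseline Day 1, and SAP 1.5 starts completers' treatment duration at the baseline visit, as if treatment began there. This stands as far as it goes. A reader might infer that many patients were already treated, but no section gives a count or a time since first dose. It does not settle the opposite either. The inclusion criterion says the treatment is ongoing, and for non-completers SAP 1.5 uses the time on drug documented at the last visit, which may include time before baseline.

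**The tables may not understate the treatment effect.** This stands. The study is uncontrolled, so the tables show within-patient change, and step 5 shows that departures can push late windows the other way. Net understatement is a tempting conclusion that the documents do not support. A second bias of unknown size does not make the pooled figure interpretable, however, and patients treated before Visit 1 affect the early windows as well.

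**No comparison between indications is planned.** This also stands. A reader might infer confounded comparisons between RA, PsA and AS. SAP 2 only breaks results down by indication, and its only named tests compare baseline data of completed and not-completed patients.

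**Part of the plan is unaffected.** Absolute values are tabulated in each window, Protocol 1 names maintenance of efficacy as a focus, and Protocol 5.1.1 allows subgroups. This helps with maintenance. It does not rescue the change and responder tables as evidence of response, and a subgroup by time on drug is permitted but not planned.

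**Conclusion.** The point holds in a limited form. Entry allows ongoing treatment of any length, and the SAP measures every change and responder table from the enrolment visit. Pre-treatment and on-drug baselines are therefore not separated. For patients already improved at Visit 1, the tables understate change from pre-treatment.

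The size cannot be derived from the documents. With f from 0.10 to 1 and r from 0.25 to 0.8, the pooled mean change runs from 0.975 of the change from pre-treatment (negligible) down to 0.20 (most of it lost). These figures assume the same eventual improvement in both groups. The BASDAI figures also rest on an assumed distribution of improvement. The understatement applies to already-treated patients only; the net direction in late windows stays uncertain. The change should be made, because the effectiveness statement depends on it and it needs only analysis.

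**What to change.** 1. **Establish treatment start.** Define the variable behind table 2.1.3 and confirm what is held. The data-collection sections of the protocol name no first-injection date as a routine field. Use the full date if there is one. Otherwise, class a patient as already treated if the start year precedes the baseline year, or use documented time on drug minus study duration where that time counts from the first dose. SAP 1.5 uses documented time for non-completers only, so check that completers have it too; if not, the split would be tied to completion.
2. **Report** time on adalimumab at baseline, by indication. State whether earlier adalimumab counts as anti-TNF experience; as written, that table cannot stand in for this one.
3. **Split** all difference-from-baseline, BSA shift, HAQ and BASDAI responder tables into patients starting at or about Visit 1 and patients already treated. Fix the cut-off in the SAP once the precision of the date is known. Base the effectiveness statement on the first group, label the second as maintenance on treatment, and keep the pooled tables as supportive.
4. **If start cannot be derived,** label the pooled results as change since enrolment and do not interpret them as response to starting treatment.

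**Cost.** One derived variable and extra columns, with no new data collection. The headline change rests on a smaller n. If only the year is held, some patients will be misclassified: a December start with January enrolment would count as already treated, and a January start with November enrolment as new. The split does not remove the selection of persisters in late windows, which should be stated beside those results.
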